2.3 Specific Aims

2.3.1 Specific Aim 1

Primary Outcome of the trial. The primary outcome for Specific Aim 1 will be time to treatment failure, with censoring at 12 months. Treatment failure occurs when recurrence of ocular inflammation is observed and/or the recurrence of joint inflammation is persistent and severe enough to necessitate unmasking to manage the arthritis recurrence. The recurrence of ocular inflammation is defined as one or more of the features in Table 1 in at least one eye:

Table 1: Criteria for Treatment Failure by Uveitis Recurrence
(at least one of the following in at least one eye)

Parameter	Definition
Anterior chamber cells*	≥2-step increase** at two separate visits ≥7 days apart >0.5+ cell observed for ≥28 days ≥3+ cell observed at a single visit
Vitreous haze***	>0.5+ haze at a single visit
Choroid & retina	Active retinal / choroidal lesions or macular edema (CST >2 standard deviations above normal thickness or cysts in 1mm central subfield) at a single visit

*SUN criteria³, **increase is based on inflammation at baseline; ***NEI vitreous haze grading scale⁴

Secondary Objectives

- To compare the proportion of people exhibiting treatment failure between the randomization groups during the first 6 months and during the first 12 months of study duration.
- To compare the cost-effectiveness of adalimumab therapy between the randomization groups during 12 months.

Secondary Objectives with Alternative Outcomes

We propose to compare longitudinal values of specific variables between the two randomization groups. The following outcomes will be compared:

- Best Corrected Visual Acuity (BCVA) score,
- Childhood Health Assessment Questionnaire score (CHAQ)⁵ in patients ages 5+,
- EuroQol 5 Dimension Youth Survey (EQ-5D-Y)⁶ score in patients ages 4+,
- Children's Visual Functioning Questionnaire (CVFQ)⁷ score in children aged 3 to 7 years,
- Effects of Youngster's Eyesight on Quality of Life (EYE-Q)⁸ score in children ages 5+,
- Juvenile Arthritis Disease Activity Score (JADAS)⁹ values: JADAS-10 and JADAS-27,
- Estimates of anti-adalimumab antibody (ADA) levels.

We also propose to compare proportions between the two randomization groups. These proportions correspond to the time until treatment failure or censoring time of 6 months as well as until treatment failure or censoring time of 12 months. Specifically:

- The proportion of patients who exhibit an arthritis flare, as defined in the Manual of Operations Section 6.4.1.²

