We propose imputation of post-failure BCVA by *last observation carried forward* (LOCF), followed by pooled regression (clustered robust standard errors on individual). We propose to do so only when BCVA is available at the time (study visit) at which treatment failure is declared. We will use all BCVA measurements until either treatment failure or completion of the trial and report the coefficient for randomization group, adjusting for baseline antimetabolite use and country.

We also propose to descriptively report mean, median BCVA (together with standard deviation and interquartile range) of patients at each visit. Actual BCVA will be reported in a descriptive analysis.

This collection of procedures serves as a template for all continuous outcomes for which we assess final values (below).

In Aim 3, these regression models will be examined on an intent to treat basis, so time/outcomes after treatment failure are included in the analyses.

The following regression analyses will be conducted following the templates above: statistical predictor will be randomization group, and we include fixed effects for baseline antimetabolite and country. A separate model will include country by treatment interaction. Treatment effects will be only reported by stratum when heterogeneity or interactions are found.

Final values of the following continuous outcome variables will be modeled following the template found above in this Planned Secondary Analyses with Alternative Outcomes section:

- **The CHAQ score**
 - For this quality-of-life measurement and the three specified immediately below, a separate analysis comparing the patient's baseline value with their value at the time of failure, 6 and 12 months will be considered.
- **The EQ-5D-Y score**
- **The CVFQ score**
- **The EYE-Q score**
- **The JADAS-10 and JADAS-27 scores**
- **Estimated ADA levels**

Final values of the following binary outcome variables will be modeled with log binomial regression following the similar template in the Planned Subsidiary Analyses of the Primary Model section:

- **The proportion of patients who exhibit one or more arthritis flares**
- **The proportion of patients who achieve an improvement in JADAS-10**
- **The proportion exhibiting macular edema**

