For continuous outcomes, plots of each measurement along with the outcome status will be prepared for each patient. Plots will include data for patients after any treatment failure, in a different color. We plan to separately examine patients using antimetabolites at baseline and those who were not. We will conduct linear mixed effects regression for these longitudinal outcomes, using time dependent covariates. The continuous variables of interest are:

- BCVA
- CHAQ score
- EYE-Q score
- JADAS-10 and JADAS-27 scores

Application of LASSO procedures to linear mixed models will be conducted with the R package `glmmlasso`.

Finally, a similar exploratory analysis will be used for the time to treatment failure (as defined earlier), again using LASSO regression with the same set of covariates. LASSO model selection will be implemented using the R package `coxnet`. We note that other model selection procedures (such as backwards stepwise regression) can be considered, provided uncorrected significance P-values are not reported after model selection.

3.1.3 Specific Aim 3

Primary analysis. The outcome variable is the proportion of people achieving corticosteroid-sparing controlled ocular inflammation at month 12 of the study. We propose log binomial regression, with randomization group as a covariate and fixed effects for baseline antimetabolite use and country. The analysis will follow the same template as in Specific Aim 1 for analysis of binary outcomes (including assessment of homogeneity by country). A linear binomial regression, with the identity link, will be used to calculate risk differences between groups. Significance will be assessed with a two-sided alpha of 0.05. The distinction between the analyses in Aims 1 and 3 are that in Aim 1, outcomes are reported at 6 and 12 months, censoring at treatment failure, while in Aim 3, outcomes are reported by intent-to-treat at 6 and 12 months, regardless of treatment changes in the event of treatment failure. We propose to use Firth bias correction in this log binomial regression, and additional information is provided below.

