Analysis following the interim. Given the DSMC's decision on February 14, 2024 to stop enrollment but continue follow-up, a Cox proportional hazards regression for time to regaining control after treatment failure will be conducted as not all patients had reached month 12 at the interim. Two outcome variables for regaining control will be part of the planned analyses: time to initial control and time to sustained control. Time to initial control is defined as the first instance of meeting control criteria (as defined in Section 2.3.3) following the declaration of treatment failure. Time to sustained control is defined as the first instance of meeting control whereafter control is maintained through their month 12 visit, as it is possible that patients who experience failure will regain control, but then flare again. At the interim, participants who had experienced treatment failure will be included in the time to initial control analysis. Only patients who experienced treatment failure and had completed their month 12 visit by interim will be included in the time to sustained control analysis. When 12 month follow up is complete for all patients, all patients can be included in the pre-specified sustained control analysis.

Planned Secondary Analyses

Continuous outcome variables and binary outcome variables will be examined on an intent-to-treat basis in a similar way as indicated in Specific Aim 1. The following are planned analyses:

- **The BCVA at 6 and 12 months**, a continuous outcome,
- **The proportion of people exhibiting an arthritis flare during the first 6 months and during the first 12 months**, a binary outcome
- **The CHAQ score at 6 and 12 months**, a continuous outcome.

Planned Subsidiary Analyses

We propose to conduct the primary analysis and planned secondary analyses (as described above) using the subgroup of people who were randomized to discontinue adalimumab, subsequently had treatment failure, and then restarted adalimumab. We

will also conduct exploratory analyses to find predictors of reestablishing control of inflammation. The exploratory procedures described in Specific Aim 2 will be used (including descriptive tabulations, graphical exploration, and model selection using LASSO or other procedures). As before, exploratory analyses will always be labeled as such, and all analyses conducted will be reported.

Using procedures analogous to those in Specific Aim 1, we will also examine on an intent to treat basis:

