- **The CVFQ score.** For sample size planning, we assume a T-test comparing change scores between the randomization groups. Assuming a standard deviation of 1.70 based on a validation study of the CVFQ,³² a total sample size of 118 and assumed 10% loss to follow-up by 12 months provides 80% power to detect a mean difference of 0.93 points.
- **The EYE-Q score.** For sample size planning, we assume a T-test comparing change scores between the randomization groups. Assuming a standard deviation of 0.75,⁸ the total sample size of 118 and assumed 10% loss to follow-up by 12 months provides approximately 80% power to detect a mean difference of 0.41 points.

- **The JADAS-10 score.** As before, we use a T-test comparing change scores between the two groups for sample size planning. Assuming a standard deviation of 8.23,¹⁰ the total sample size of 118 and assumed 10% loss to follow up by 12 months provides approximately 80% power to detect a mean difference of 4.5 points.
- **The JADAS-27 score.** Similarly, assuming a standard deviation of 8.16,¹⁰ the sample size of 118 and assumed 10% loss to follow-up by 12 months provides approximately 80% power to detect a mean difference of 4.5 points.
- **The ADA levels.** Assuming a standard deviation in ADA levels of 10,³³ the total sample size of 118 (and, the 10% assumed loss to follow-up by 12 months) suggest approximately 80% power to detect a difference of 5.5 in ADA serum levels in $\mu\text{g/mL}$.
- **The proportion of people with arthritis flares.** We assume (for sample size assessment) a test of proportions between the two randomization groups. Based on prior research, we expect 1% of those who continue adalimumab to have a flare by 6 months.²⁶ We anticipate 80% power to detect a difference of approximately 16% in the proportion of individuals experiencing arthritis flares among those who discontinue adalimumab (assuming a total sample size of 118 and 10% loss to follow-up by 12 months).
- **The proportion of patients who achieve an improvement in JADAS-10.** Assuming that 85% of those continuing on adalimumab will have an improvement in JADAS-10 score from baseline,³⁴ a total sample size of 118 (and 10% assumed loss to follow-up) provides approximately 80% power to detect a difference of at least 26% in the proportion of patients achieving an improvement between treatment groups.

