- **The proportion of people with macular edema.** We anticipate at most 1% of the individuals continuing treatment to develop macular edema, given its absence at baseline. We anticipate approximately 80% power to detect a difference of 15% (in absolute terms) in macular edema in the discontinuation arm (given 118 subjects).

The analyses for censoring at 6 months are similar to 12 months, with small decreases in detectable effect sizes due to assuming slightly shorter follow-up by month 12.

3.3.2.2 Specific Aim 2

Specific Aim 2 is exploratory, and is hypothesis generating. However, we present selected power analyses to illustrate the sufficiency of the sample size of the trial—fixed in Specific Aim 1—to inform regression models of the exploratory outcomes in Specific Aim 2.

For modeling the effect of the potentially predictive biomarker MRP8/14, we assume a

median split as a guide to power. Assuming approximately 50 uveitis flares among our patient population, we anticipate 80% power to detect a difference in MRP8/14 levels of 140 ng/ml (assuming a standard deviation of 250 ng/ml, based on previous studies).^{35,36}

For modeling the number of missed study treatment doses in the first 12 months, we anticipate over 80% power to detect a difference of 2.8 missed doses between the discontinuation and continuation groups (assuming 118 patients enrolled, and a standard deviation of 5).

For the time to failure outcome within 12 months, we anticipate 88% power to detect a hazard ratio of 2.0 between patients taking antimetabolites at baseline and those not using antimetabolites, assuming approximately equal numbers in each group (assuming 10% loss to follow-up).

3.3.2.3 Specific Aim 3

Primary Analysis

The proportion of people who achieved corticosteroid-sparing controlled ocular inflammation (Table 2) by month 6 of the study based on treatment intervention. For sample size planning, we assume a test of proportions between the two randomization groups. Based on prior research, we assume that 30% of those who discontinue adalimumab will have controlled ocular inflammation by month 6.²⁴ We anticipate over 80% power to detect a 29% difference between the two groups, based on 118 subjects.

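### Aim 1 counts arthritis flares and macular edema only until treatment failure and ignores time at risk, which tilts the comparison toward stopping and leaves the stated 80% power undefined

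*SAP*

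**What the plan says.** SAP 2.3.1 (Secondary Objectives with Alternative Outcomes) compares the proportions with an arthritis flare, with JADAS-10 improvement and with macular edema. Of the counting window it says: "These proportions correspond to the time until treatment failure or censoring time of 6 months", and it adds the same rule for 12 months. SAP 3.1.3 restates it: "in Aim 1, outcomes are reported at 6 and 12 months, censoring at treatment failure". For the model, SAP 3.1.1 says: "Final values of the following binary outcome variables will be modeled with log binomial regression following the similar template". The template brings in randomization group, baseline antimetabolite use and country. It has no offset for time at risk and no method for a competing event.

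SAP 3.3.2.1 gives power from a plain test of proportions. It takes a 1% flare rate by 6 months in the continue arm and states: "We anticipate 80% power to detect a difference of approximately 16% in the proportion of individuals experiencing arthritis flares among those who discontinue adalimumab", with 118 patients and 10% loss by 12 months. For macular edema it states "We anticipate approximately 80% power to detect a difference of 15" percentage points, against at most 1% when continuing. Neither line mentions the cut at failure.

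Aim 3 keeps time after failure: "in Aim 3, outcomes are reported by intent-to-treat at 6 and 12 months, regardless of treatment changes in the event of treatment failure". Its planned analyses include "The proportion of people exhibiting an arthritis flare during the first 6 months and during the first 12 months" and, among the subsidiary analyses, macular edema over 6 and 12 months.

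**The concern.** Treatment failure ends the count, and its timing depends on arm by design. A patient who fails at week 8 and flares at week 20 enters the Aim 1 regression as a patient without a flare, exactly like one observed for the whole window. The arm that fails sooner therefore shows fewer flares at the same arthritis hazard.

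The SAP recognizes this problem for other outcomes. For BCVA, SAP 3.1.1 says that using only the available data is expected to bias the inference, and it adds a joint model for informative missingness due to failure. The binary outcomes get no counterpart.

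At stake is the direction of the joint result. A relative risk below 1 for stopping, printed with a 95% confidence interval, could be read as reassurance about arthritis after withdrawal when it reflects only shorter observation. A reader planning from the stated 80% power could also expect more from this comparison than it can give.

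**Working it through.** **Inputs.** Failure medians of 10 weeks (stop) and 20 weeks (continue), SAP 3.3.1. Windows of 24 and 48 weeks, Protocol 1.3. Flare risks of 1% and 17% (1% plus 16 points) and 118 patients with 10% loss, about 53 per arm, SAP 3.3.2.1. Two-sided 0.05 is stated for the primary calculation and assumed here. Constant hazards and independent flare and failure times are also assumed.

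**1. The plan's own figure.** For 1% vs 17% with 53 per arm and no truncation, exact enumeration gives 79% (Fisher), 90% (score) and 93% (likelihood ratio). The pooled normal formula gives 83%. Fisher reproduces the stated 80%.

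**2. Time at risk.** The failure hazards are λ = ln 2/10 = 0.0693 and ln 2/20 = 0.0347 per week.
- Failed by week 24: 1 − 2^(−24/10) = 81% vs 1 − 2^(−24/20) = 56%. By week 48: 96% vs 81%.
- Mean time at risk, (1 − e^(−λT))/λ: 11.7 vs 16.3 weeks to week 24, and 13.9 vs 23.4 weeks to week 48.

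**3. Equal true risk of 17%.** The flare hazard is h = −ln(0.83)/T, and the counted proportion is h/(h+λ) × (1 − e^(−(h+λ)T)).
- T = 48, h = 0.00388. Stop: 0.00388/0.0732 × (1 − e^(−3.51)) = 5.1%. Continue: 0.00388/0.0385 × (1 − e^(−1.85)) = 8.5%. Ratio 0.61.
- T = 24, h = 0.00776. Stop: 0.00776/0.0771 × (1 − e^(−1.85)) = 8.5%. Continue: 0.00776/0.0424 × (1 − e^(−1.02)) = 11.7%. Ratio 0.73.
- The chance that Fisher's test declares a significant benefit of stopping is about 4% at either window.
- If the continue arm rarely fails (assumed median 300 weeks), the ratios are 0.51 and 0.32, and that chance is 15% at 6 months and 32% at 12 months.

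**4. Power if 1% and 17% are full-window risks.**

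| Window | Counted, continue vs stop | Fisher | Score | Likelihood ratio |
|---|---|---|---|---|
| 24 weeks | 0.7% vs 8.5% | 22% | 51% | 66% |
| 48 weeks | 0.5% vs 5.1% | 4% | 23% | 41% |

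Under truncation, 80% Fisher power needs a true stop-arm risk of about 32% (6 months) or 48% (12 months).

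**5. Dependence on the assumptions.** If half of the otherwise missed flares are found at the failure visit, Fisher power is 55% and 43%. If flare and failure times are positively correlated (Gaussian copula, 0.3) and flares at that visit do not count, it is 8% and under 1%.

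**6. Does a competing-event display help?** The formula in step 3 is the cumulative incidence of flare with failure as a competing event. A cumulative incidence comparison therefore returns the same 5.1% vs 8.5%. A cause-specific hazard comparison does not carry the bias, because patients leave the risk set when they fail. Its log-rank power for 17% vs 1%, by simulation, is about 68% at 6 months and 43% to 45% at 12 months. Expected events are 53 × (0.0849 + 0.0068) = 4.9 and 53 × (0.0515 + 0.0049) = 3.0.

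**The case against.** **Aim 3 already does this.** SAP 2.3.3 and 3.1.3 compare both outcomes by intent-to-treat over all follow-up, and 3.1.3 states openly how the two Aims differ. It would be wrong to infer that the plan has no comparison free of truncation. What stands is that the plan does not say which version leads, and the two could point in different directions.

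**These are minor analyses.** SAP 3.1.1 ranks them below the primary outcome, and SAP 3.5 makes them descriptive. Enrollment stopped in February 2024, so restated power no longer affects recruitment. This lowers the weight of the point. It does not make a biased relative risk harmless.

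**The power line may be right.** A reader might infer that power simply collapses to some fixed low figure. The documents do not support that. The result depends on the test and the window, and on reading the 16 points as a full-window difference. Read as a difference in the proportion that Aim 1 defines, 80% stands. Nor is it a 12-month calculation on its face: the 1% is given by 6 months.

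**Events at the failure visit are seen.** Joints are examined there, and arthritis that cannot be managed is itself a failure (Protocol 7.1, 8.1). This is a fair limit on the loss. But Protocol 3.1 dates failure at the initial threshold visit, while the Treatment Failure visit may come 7 or 28 days later. Whether a flare found then counts is not stated. The first scheduled joint examination after baseline is Month 3, later than the stop arm's planned 10-week median.

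**Edema is a failure criterion.** This is correct. Edema that comes first, or is present at the failure visit, is captured. Only edema after another type of failure is lost, so applying the arthritis figures to edema would overstate the effect.

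**Conclusion.** The concern holds for arthritis flare and, to a smaller degree, for macular edema. Aim 1 compares proportions over windows whose length depends on arm, without adjustment, and the bias favors stopping. Under the SAP medians and independent times, equal 17% risks give ratios of 0.73 (6 months) and 0.61 (12 months).

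A reader might go further and expect a statistically significant false benefit. Under those medians that is unlikely, about 4%. It becomes material only if the continue arm rarely fails. That case is assumed here, although SAP 3.3.1 itself calls its 20-week median conservative.

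The 80% power line is not shown to be wrong. It is undefined until the SAP says whether the 16 points are truncated or full-window. On the full-window reading, power is about 22% to 66% at 6 months and 4% to 41% at 12 months, and higher if flares found at the failure visit count. The intent-to-treat version in Aim 3 limits the harm.

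**What to change.** 1. Name the existing Aim 3 intent-to-treat comparison, with all follow-up to month 12, as the lead between-arm result for arthritis flare and macular edema. It answers the strategy question, because treatment may change after failure.
2. In Aim 1, replace the log binomial comparison of these two outcomes by a cause-specific Cox model that censors at failure from other causes. State that events found at the failure visit count, and how they are dated relative to the failure date.
3. Show cumulative incidence only as description, and say that it does not remove the difference in time at risk.
4. Restate the arthritis and edema power lines in SAP 3.3.2.1 for the analysis kept, and say whether the differences are full-window or truncated.

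The cost is SAP wording; the plan already follows patients through Month 12 after failure. The change should be dated as made after the interim unmasking.

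The downside is that the Aim 1 model rests on few events, about 3 to 5 in the 17% vs 1% scenario. At 12 months the continue arm would have none in about 77% of trials (0.9951^53), so the interval needs a method that tolerates an empty arm. The stated power also becomes less favorable.

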2.4 Randomization

2.4.1 Stratification

We propose stratification by country and use of antimetabolite medication. Within each stratum, assignments will be conducted using a randomly permuted block randomization scheme.

Patients will be enrolled in three countries: United States, United Kingdom and Australia. Patients will be recruited from fifteen to twenty study sites, with the possibility for sites to be added to meet the *fixed* sample size requirements. Patients will be randomized in a 1:1 ratio to two interventions: adalimumab or matched placebo. The treatment protocols are specified in the ADJUST Manual of Operations.

Stratification will be done by antimetabolite drug use based on a belief by the study team that concomitant antimetabolite drugs may have a differing impact on treatment outcomes of uveitis patients using TNF- α inhibitors.¹¹ Similarly, variations in the baseline demographics within each country may impact treatment outcomes with adalimumab.

